Patients will be randomized to either metformin or placebo. Metformin dose will begin with 500mg twice a day for the first two weeks and then increase to 1000mg twice a day for the remainder of the trial. In order to minimize GI side effects, the medication will be taken with a meal. The intervention will last 180 days. Prior to randomization all potential study subjects will be evaluated with complete medical history and brief physical examination, complete review of home medications, measurement of vital signs and body weight with calibrated scale, serum collection for basic metabolic panel, hemoglobin A1c and liver function test. All patients will also undergo cardiopulmonary exercise testing and transthoracic echocardiography. Patients who meet all the inclusion criteria will be required to complete the informed consent form. Patients will have 2 office visits in total, one at day 1 (baseline) and one on day 180 (final). On day 30, participants will have a blood work for basic metabolic panel, venous lactate and fasting plasma glucose for adverse event assessment (safety). On the final visit, patients will undergo repeat echo, labs and cardiopulmonary exercise testing. The timing of all procedures in this study is outlined in the table 1. Procedural timeline and further details of the relevant procedures are as follows:

Medical history and physical exam: Subjects will be asked to provide information about their basic demographics: age, gender, and race as well as previous and current health and medications. The subject will have his or her height, weight, blood pressure both supine and standing, heart rate, respiratory rate and body temperature recorded. A HF-focused physical examination will be performed and recorded. A Minnesota Living with Heart Failure Questionnaire will be completed.

Blood tests:

Blood be drawn via venipuncture. The following will be prospectively measured for every patient at the indicated time points.

- Screening: fasting insulin and glucose level, basic metabolic, liver function test and HgbA1c
- Baseline: , BNP, venous lactate
- Safety: basic metabolic panel, venous lactate and fasting glucose
- Final: basic metabolic panel, BNP

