Cardiopulmonary Exercise Test (CPET): At baseline and final visit. The CPET is to be performed on a either a treadmill with a Medgraphics Ultima metabolic cart or a Corival CPET Ergometer (stationary bicycle) in the Cardiopulmonary Exercise Lab. All testing is to be done in the Cardiopulmonary Exercise Lab in Milstein, a clinical cardiopulmonary exercise testing laboratory. There will be a physician present at all tests, and the appropriate emergency equipment and trained personnel are available should difficulties arise during the exercise test. The CPET will be conducted per ATS and AHA guidelines (25, 26). For a treadmill test: Participants will exercise on a treadmill at an increasing rate of 0.1MPH per minute and 1% grade per minute starting at a speed of 1.0 MPH at 0% grade. For a bicycle test: The participants will perform a 15 watt ramp protocol and instructed to pedal to a rate of 50-60 rpm. The protocol begins at zero watts and will increase in resistance by either 15 watts/minute (for female patients) or 20 watts/minute (for male patients) Heart rate, BP and perceived exertion score (RPE, reported on a scale from 0-10.0) will be recorded in one-minute intervals. Oxygen consumption (VO2) (ml/min), Carbon Dioxide production (VCO2) (ml/min), and minute Ventilation (VE) (L/min) will be measured on a

breath by breath basis. Peak VO₂, VE/VCO₂ and respiratory exchange ratio (RER) will be computed.

Biobank: Serum samples will be stored in a biobank repository in the CCTI Biobank Core Facility. The purpose of this biobank is to characterize serum biomarkers of patients with heart failure who have been exposed to metformin versus placebo. The registry will include previously gathered clinical information in electronic medical records. This data includes demographics, clinical comorbidities, hemodynamics, echocardiographic indices of structure and function, hospitalizations, medication use and laboratory data. All specimens/data will be distributed at the discretion of the principal investigator. The purpose of this dissemination will be for experimental collaboration. We will review to make sure collaborators have an existing approved IRB before we distribute. The proper MTA will be executed prior to delivery of samples. All samples will be coded so the recipient will not have any direct patient identifiers linked to these samples.

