Clinical Data Collection: This study will collect all data obtained during routine clinical care of all patients who participate in this study. Retrospective data will be collected. All patients will be followed prospectively until death. Trained research staff will extract data from electronic medical records. We will acquire longitudinal clinical information, including complications, hospitalizations, medication use, laboratory values, echocardiographic data, hemodynamic data, as well as mortality.

Table 1: Procedural Timeline

Day Number	0	30	180	210
Type of Visit	Screening/Baseline	Safety	Final Visit	Safety Follow
Informed Consent	X			
Medical History	X			
Vital Signs	X			
MLHFQ	X		X	
Physical Exam	X		X	
Adverse Event		X	X	X
Pregnancy Test	X		X	
Basic Metabolic Panel	X	X		
Fasting Plasma Glucose	X	X	X	
Fasting Insulin Level	X			
Hepatic Function Panel	X			
BNP	X		X	
Hemoglobin A1c	X		X	

Venous Lactate	X	X	X	
VAS and Likert Scale	X		X	
Echocardiogram	X		X	
Venous Reactivity	X		X	
CPET	X		X	
Study Med Allocation	X			
Biomarker Blood Samples	X		X	
PET Substudy				
13N-Ammonia	X		X	
18F-FDG	X		X	

Primary Endpoint Rationale: The primary endpoint is a change in the slope of the ventilation versus carbon dioxide production (VE/VCO₂). Peak VO₂ has been considered in heart failure literature as a strong predictor for HF outcomes and was the original variable studied in that population. However, a confounder with metformin is that in normal patients without heart failure, metformin treatment has been shown to slightly decrease VO₂(27). The mechanism behind this is possible direct inhibition of complex I of the mitochondrial electron transport system(28). The slope of the relationship between minute ventilation and CO₂ production (VE/VCO₂) has been also thoroughly studied in systolic heart failure as a marker of ventilator efficiency and overall prognosis(29). As demonstrated in over 20 papers (summarized in reference 29) and in the AHA guidelines (26), the VE/VCO₂ slope more powerfully predicts mortality, hospitalization or both than peak VO₂. This has been shown to be a sensitive index of cardiorespiratory fitness in patients taking metformin with insulin resistance and heart failure and is not confounded by any inhibitory interactions between metformin and the variable (30). Thus we have excluded peak VO₂ as a primary endpoint and will instead use VE/VCO₂ as the primary endpoint for power analysis.

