The main known adverse reaction to metformin is lactic acidosis. Metformin associated lactic acidosis (MALA) is exceedingly rare and is manifested as nonspecific symptoms such as malaise, myalgias, abdominal pain, respiratory distress, or increased somnolence. The incidence of MALA is exceedingly rare approximately 0.03 to 0.06 per 1000 patient years (32). In post marketing data analysis, there have been 47 documented MALA events in 1 million users. Metformin-associated lactic acidosis is characterized by elevated blood lactate concentrations (>5 mmol/L), anion gap acidosis (without evidence of ketonuria or ketonemia), and an increased lactate:pyruvate ratio. According to FDA insert, metformin associated lactic acidosis primarily occurs in patients with renal impairment. Thus to minimize the risk of adverse, we have added a safety time point to measure renal function during the course of the study. We will follow guidelines from the FDA which limit initiation of Metformin to patients with GFR's over 45 ml/min*1.73m² (23). If the GFR drops to between 30 and 45 ml/min*1.73m², despite the fact that the FDA allows continuation of metformin until a GFR of 30 ml/min*1.73m² we will dose reduce to 1 gram total per day of study drug as per American Diabetes Association Guidelines(33).

Study drug treatment will be discontinued in the following situations: 1) when subject withdraw consent, 2) in case of pregnancy, 3) when subjects develop severe renal dysfunction (defined as estimated GFR <30 ml/min*1.73 m²), or 4) when subjects develop a condition which, in the investigator's judgment, precludes further therapy (please see Data Safety Monitoring Plan). Temporary discontinuation of the drug will occur if the patient is to undergo a procedure that include iodinated contrast agent that could affect renal function. Discontinuation will have no consequence on regular patient care. There will be no dose modifications of the study medication as there is none indicated by the FDA.

Blood Draw: Phlebotomy is a commonly used medical procedure for screening and follow-up of disease. Efforts to decrease the risks associated with blood draws include using highly experienced staff, applying external pressure to the site of the blood draw for a specified time following the draw, and the use of aseptic technique throughout the procedures. The amount of blood phlebotomized for analysis (20 mL) is not anticipated to be associated with significant risk.

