Congenital Abnormality	Pregnancy is an exclusion criteria for this study and patients will be advised not to become pregnant during this study. However, if we detect a pregnancy that occurs during the study (there is a pregnancy test at the end of study), we will stop the study for that patient. We will mandate that we follow the patient until after birth to determine if there is a congenital abnormality. If we detect this event, the DSMB will be required to unblind the allocation (if the trial is ongoing) and determine if the congenital abnormality is related to the study drug.
Hospitalization	Discontinuation of study drug if it is either 1) unsafe to continue for medical reasons by either the treating physicians, the PI of the study, or the DSMB, or 2) if it deemed by the DSMB to be related to the study drug. The DSMB will unblind the allocation and determine if the hospitalization is related to the study drug.
Venous Lactate rises to $>2\text{mmol/L}$	Discontinue study drug, de-identification of study medication. Repeat lactate daily until normalizes. Contact primary cardiologist. Consider inpatient hospitalization.
Fasting Serum Glucose <60mg/dL	Discontinue current regimen. Administer patient oral glucose. Repeat value until normalizes. Referral to primary physician/cardiologist. Referral to ED if for referral or assessment if symptomatic and non-responsive to glucose tabs.

Renal Impairment for already enrolled patients

Glomerular Filtration Rate	Action
GFR \geq 45ml/min/1.73m ²	No action
GFR 30 - 44ml/min/1.73m ²	Reduce total dosage to 500mg twice a day. Schedule follow up basic metabolic panel in 3 months if GFR measurement occurs >3 months from scheduled end of trial. If follow up GFR is greater than 45 ml/min/1.73m ² , then patient can revert dosage to 2 grams per day. If GFR is less than 30 ml/min/1.73m ² , study drug and patient enrollment will be terminated.
GFR <30ml/min/1.73m ²	Stop Drug and patient enrollment in trial

5. Reporting of adverse events/adverse drug reactions

Adverse events (AEs) will be reported to the IRB and the DSMB. Adverse events will be reported on a weekly basis to the DSMB and serious adverse events will be reported to the IRB and DSMB within 24 hours of being detected.

6. Who will review AEs and other safety data?

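### At GFR <30 the renal table ends trial enrollment as well as study drug, so read literally such a patient would miss the only scheduled post-baseline CPET, which measures the primary endpoint

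*Combined protocol and SAP*

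**What the plan says.** The table for renal impairment in enrolled patients (Data and Safety Monitoring Plan, item 4) covers GFR <30 in two rows.

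- **GFR 30-44 row.** The dose is halved and a recheck is arranged: "Schedule follow up basic metabolic panel in 3 months if GFR measurement occurs >3 months from scheduled end of trial". If GFR is then below 30, "study drug and patient enrollment will be terminated".
- **GFR <30 row.** "Stop Drug and patient enrollment in trial".

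The Study Drug paragraph under Specific study risks has its own list of reasons for discontinuing study drug. It includes the same threshold, "when subjects develop severe renal dysfunction (defined as estimated GFR <30", and says nothing about enrollment or later visits.

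On measurement, Study Intervention and Procedures states: "Patients will have 2 office visits in total, one at day 1 (baseline) and one on day 180 (final". It adds: "On the final visit, patients will undergo repeat echo, labs and cardiopulmonary exercise testing". The exercise test paragraph agrees: "Cardiopulmonary Exercise Test (CPET): At baseline and final visit". In "Table 1: Procedural Timeline", the CPET, echocardiogram, BNP, MLHFQ and VAS/Likert rows are marked at days 0 and 180 only.

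The Statistical Approach keeps every randomized patient in the analysis whether or not the protocol is completed. It uses last observation carried forward when a patient is lost to follow-up and the final outcome cannot be assessed.

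**The concern.** Stopping metformin at GFR <30 is a sound safety rule. Ending enrollment is a separate act that safety does not require, and the protocol gives no reason for it. The rows for life-threatening illness, hospitalization and raised lactate in Table 2 tell staff to discontinue study drug and do not mention enrollment, so the renal rows go further.

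If the rows are followed as written, the primary outcome would be missing because of a protocol instruction and after a health event, although the visit that measures it is already planned. An intention-to-treat analysis needs that measurement in patients who stopped treatment. Without it, their inclusion rests on an assigned number.

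**Working it through.** The plan gives no figure on this point, so the check sets the sections side by side and adds simple counts.

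**1. When the rule can act before day 180.** Item 2 of the Data and Safety Monitoring Plan schedules creatinine at days 0, 30 and 180. Taking 3 months as 90 days:

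- Day-30 test: 180 − 30 = 150 days remain. Since 150 > 90, a GFR of 30-44 on that day leads to the recheck.
- Recheck: 30 + 90 = day 120, so 180 − 120 = 60 days remain.
- Unscheduled clinical test: any day.
- Value first found on day 180: need not cost the CPET.

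**2. What such a patient would miss.** Endpoints are as listed on the opening page. Other routes are those in Clinical Data Collection, Clinical Events and the safety-test list.

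| Endpoint | Scheduled post-baseline measure | Other route in the documents |
|---|---|---|
| Primary: VE/VCO₂ | CPET, day 180 | none |
| a) Decompensation | three-monthly contacts | telephone or records |
| b) MLHFQ | day 180 | none evident |
| c) LVEF | echo, day 180 | clinical records possible |
| d) GLS and GCSR | echo, day 180 | none evident |
| e) BNP | day 180 | clinical records possible |
| f) Body weight | not counted: the safety list has day-30 vital signs, which may include weight | – |
| g) Dyspnea scores | day 180 | none evident |
| h) Peak VO₂ | CPET, day 180 | none |

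The scheduled day-180 measure is missed for the primary endpoint and for six of eight secondary endpoints (b, c, d, e, g, h). Two of the six (c, e) might be recovered from records, which leaves 6 − 2 = 4 with no evident route (b, d, g, h).

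**3. Heart failure contacts.** With contacts at about days 90 and 180, two are still due after a day-30 stop and one after a day-120 stop. The renal rows do not rule these out, but they do not secure them.

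**4. The value that enters the analysis.** The only CPET on file is the baseline one, so carry-forward gives change = baseline − baseline = 0. This assumes carry-forward is applied at all. Its trigger is loss to follow-up, which does not clearly describe a patient whom the protocol itself removes.

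**5. Size.** Entry requires eGFR ≥45. Reaching <30 takes a fall of more than 45 − 30 = 15 ml/min, or more than 15/45 = 33% from the entry floor. Each case is 1/25 = 4% of an arm and 1/50 = 2% of the trial. The number of cases is not given and runs from zero upward.

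**The case against.** The case on the other side has four parts.

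- **The trigger is narrow.** It takes a large fall in GFR, and the scheduled chances to detect it before day 180 are the day-30 test and a recheck for those at 30-44. This stands, and it limits the weight of the point.
- **The rows may be loose wording.** They do not mention the day-180 visit, the risk paragraph stops drug only, and Clinical Events and Clinical Data Collection follow subjects without stating an exception. This stands in part: staff might still invite the patient. But both rows name drug and enrollment together, and neither follow-up section provides a CPET.
- **The analysis plan already covers it.** The patient is imputed and not dropped. That is so, but inclusion is not measurement. The sensitivity analyses also only assign values, and they are worded for weight loss.
- **The benefit is unproven.** How far a CPET after up to 150 days off drug would differ from zero change is unknown. This stands. The reason for collecting it is that intention-to-treat calls for the measured value.

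A reader might also infer three stronger things that the documents do not support. The renal rows do not contradict the intention-to-treat statement; they weaken what it rests on. Not all six secondary endpoints are certainly lost, because records may hold LVEF and BNP. Nor is day 180 beyond doubt the only later office visit: Clinical Events allows three-monthly recording at office visits or by telephone. What is clear is that day 180 carries the only scheduled post-baseline CPET.

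**Conclusion.** The point holds and is minor. Both renal rows end enrollment at GFR <30, and no section keeps such a patient for the day-180 CPET. Read literally, a patient stopped at day 30, at the recheck or on an unscheduled test before day 180 would have no post-baseline primary endpoint or peak VO₂, and would miss the other scheduled day-180 measures. The patient would enter the primary analysis with an assigned value, which is zero change if carry-forward is applied.

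The conclusion rests on the literal wording of the two rows and on 3 months being about 90 days. The number affected is unknown, probably small and possibly zero.

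It is tempting to infer lost power or a diluted treatment effect. The documents give no rate of GFR <30, and any such calculation would also have to assume how much effect persists after the drug is stopped. Neither consequence is claimed.

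**What to change.** Keep every drug-stopping threshold, and make three edits:

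- 30-44 row, on a repeat GFR below 30: *study drug will be terminated*.
- <30 row: *Stop study drug*.
- Add: *A patient who stops study drug because GFR is <30 remains in the trial, unless consent is withdrawn, for ADHF-event contacts to day 180 and for the planned day-180 visit, with echo, BNP, MLHFQ and dyspnea scales in all such patients, and CPET as well unless judged unsafe.*

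The sentence applies only to stops for GFR <30, so it leaves the other Table 2 rows as they are. The PET sub-study scans are unchanged.

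The cost is two reworded rows, one sentence and a few already planned day-180 visits in patients who are off drug. No new procedure is needed. Those day-180 values will reflect assigned treatment and not time on drug, which is what the intention-to-treat analysis asks for.
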